**Table 8: Laboratory Adverse Event Grading Scale (continued)**

Parameter	Grade 1/Mild	Grade 2/Moderate	Grade 3/Severe	Grade 4/ Potentially Life-Threatening
change from baseline				
Platelets decrease – $\times 10^3/\mu\text{L}$	125 – 140	100 – 124	25 – 99	< 25
Leukocytes (WBC) increase – $\times 10^3/\mu\text{L}$	10.80 – 15.00	15.01 – 20.00	20.01 – 25.00	> 25.00
Leukocytes (WBC) decrease – $\times 10^3/\mu\text{L}$	2.50 – 3.50	1.50 – 2.49	1.00 – 1.49	< 1.00
Lymphocytes decrease – $\times 10^3/\mu\text{L}$	0.75 – 1.00	0.50 – 0.74	0.25 – 0.49	< 0.25
Monocytes increase – $\times 10^3/\mu\text{L}$	1.01 – 2.00	2.01 – 3.00	> 3.00	Intervention indicated
Basophils increase – $\times 10^3/\mu\text{L}$	0.16 – 0.50	0.51 – 0.80	> 0.80	Intervention indicated
Eosinophils increase – $\times 10^3/\mu\text{L}$	0.65 – 1.50	1.51 – 5.00	> 5.0	Hyper-eosinophilic
Neutrophils decrease – $\times 10^3/\mu\text{L}$	1.50 – 2.00	1.00 – 1.49	0.50 – 0.99	< 0.50
Coagulation				
Prothrombin Time – sec	11.2 – 12.3	12.4 – 13.4	13.5 – 14.0	> 14.0
Activated Partial Thromboplastin Time (aPTT) – sec	35.0 – 42.0	42.1 – 49.0	49.1 – 52.5	> 52.5
Urine Dipstick				
Nitrite	1+	2+	>2+	--
Urine Protein	Trace	1+	2+	Hospitalization or dialysis
Urine Glucose	Trace	1+	2+	Hospitalization for hyperglycemia
Urine Microscopy				
White blood cells (WBC) per HPF	0 – 10	11 – 50	> 50 or gross	Hospitalization or intervention
Red blood cells (RBC) per HPF	1 – 10	11 – 50	> 50 or gross	Hospitalization or packed red blood cells (PRBC) transfusion
Bacteria (microscopic)	Few	Moderate	Many	Hospitalization or intervention

 Liver function tests (LFT) include ALT and AST. Urine microscopy was only performed if urine dipstick was abnormal for blood, protein, glucose, and nitrites. The results of the urine microscopy would supersede the results of the urine dipstick.

**Table 9: ECG Adverse Event Grading Scale**

ECG interval abnormality	Grade 1/Mild	Grade 2/Moderate	Grade 3/Severe	Grade 4/ Potentially Life- Threatening
QTcF interval prolonged (msec): • Male • Female	Asymptomatic, QTcF • 451 – 479 msec • 471 – 479 msec	Asymptomatic, QTcF 480 – 500 msec OR increase in interval 30 – 59 msec above baseline	Asymptomatic, QTcF >500 msec OR Increase in interval >60 msec above baseline	QTcF >500msec, Life threatening signs or symptoms (e.g., arrhythmia, hypotension, syncope); Torsade de pointes
PR interval prolonged (msec)	211 – 250 msec	>250 msec	Type II 2 nd degree AV block OR Ventricular pause >3.0 msec	Urgent Intervention indicated

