- **Vital Signs (VS) inclusive of orthostatic blood pressure and heart rate:** Include body temperature (oral), BP (resting more than 5 min), RR, and HR. Heart rate and BP will be measured at rest with the participant supine for at least 5 minutes. VS will be measured twice daily within 30 min before and 2h (\pm 10 min) after each dose on Days 1 to 7, once daily in the morning on Days 8 and 9, or at ET. Abnormal VS may also be measured at unscheduled visits as needed for follow up of AEs. Repeat measurements with the participant supine may be allowed if the first measurement is abnormal (See [Section 8.3.3](#)).¹

Note 1: Orthostatic blood pressure and heart rate will be obtained and recorded after the supine VS, while the participant is in the standing position with measurements taken at 1 minute \pm 15 seconds and 3 minutes \pm 15 seconds after standing.

- **ECG:** A standard 12-lead ECG will be recorded, within 30 min before the morning dose on Day 4, on Day 8 before the 12h blood (plasma) PK collection after the evening dose on Day 7, or ET. Additional ECGs may be recorded as needed for the evaluation of TEAEs. The participant should be in a supine position and should have an approximate 10-minute rest period prior to ECG recordings.

A physician (PI or coinvestigator) or clinician who is licensed to make diagnoses (listed on Form FDA 1572) will evaluate the ECG for any abnormalities in ECG intervals including QT/QTcF, and any morphologic abnormalities for clinical significance. If a question regarding ECG interpretation arises, the study investigators will have the ECG reviewed by a cardiologist.

8.3.2 **Laboratory Evaluations**

- **Clinical Laboratory Assessments:**

- Blood for HEM, CHEM, and COAG will be collected before the morning dose on Days 2, 4, and 6, and on Day 8, or ET for the evaluation of the same tests listed in [Section 8.1.2](#). Clinical lab tests may also be performed at unscheduled visits as needed for follow up of AEs. Participants must be fasting at least for 4 h before any blood draw for clinical laboratory assessments.
- UA will be collected before the morning dose on Day 4 and on Day 8, or ET (See [Section 8.1.2](#))

8.3.3 **Procedures to be Followed in the Event of Abnormal Clinical Laboratory Test Values or Abnormal Clinical Findings During Conduct of the Trial**

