12. APPENDICES

APPENDIX A: ADVERSE EVENTS TOXICITY GRADING CRITERIA

The Toxicity Grading Scale for Healthy Adult and Adolescent Volunteers Enrolled in Preventive Vaccine Clinical Trials will be used in this protocol, available at the following link: <https://www.fda.gov/media/73679/download>.

Supplemental Toxicity Tables

Vital Signs

Parameter	Grade 1	Grade 2	Grade 3	Grade 4
Sinus Bradycardia – when baseline HR <60 bpm ¹	45 – 49 bpm	40 – 44 bpm	<40 bpm	Life-threatening consequences, urgent intervention indicated

¹Use clinical judgement when characterizing bradycardia among some healthy subject populations (e.g., conditioned athletes).

Note: Isolated/individual abnormalities of VS would not be considered toward halting criteria. Abnormalities of VS will be described as “increased X” or “decreased X” (X = HR, BP, RR, temperature) if asymptomatic, transient, and not associated with a systemic or organ-specific disorder and coded by MedDRA within the System Organ Class (SOC) “Investigations.” These abnormalities will be graded per criteria in this table, but not considered in determining whether study stopping criteria have been met. On the other hand, abnormalities of VS that are either secondary to systemic or organ-specific clinical syndrome or primary disorders will be coded in the appropriate SOC (e.g., “cardiac disorders”, “respiratory disorders”, “immunological disorders”, etc.). These abnormalities will be considered in determining whether stopping criteria have been met.

Laboratory Parameters

Hematology	Grade 1	Grade 2	Grade 3	Grade 4
Monocytes increase, All ages – $\times 10^3/\mu\text{L}$	1.01 – 2.00	2.01 – 3.00	>3.00	Intervention indicated
Basophils increase, All ages – $\times 10^3/\mu\text{L}$	0.16 – 0.50	0.51 – 0.80	>0.80	Intervention indicated
Carbon dioxide increase, All ages – mEq/L	32.1 – 36.0	36.1 – 40.0	>40.0	Intervention indicated
Carbon dioxide decrease, All ages – mEq/L	17.0 – 21.9	14.0 – 16.9	<14.0	Metabolic acidosis Intervention indicated

ECG Parameters

ECG interval abnormality	Grade 1	Grade 2	Grade 3	Grade 4
QTcF interval prolonged (msec): • Male • Female	Asymptomatic, QTcF • 451 – 479 msec • 471 – 479 msec	Asymptomatic, QTcF 480 – 500 msec OR increase in interval 30 – 59 msec above baseline	Asymptomatic, QTcF >500 msec OR increase in interval >60 msec above baseline	QTcF >500 msec, Life threatening signs or symptoms (e.g., arrhythmia, hypotension, syncope); Torsade de pointes

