## 9.9. Other Safety Measures

### 9.9.1. 12-Lead Standard Electrocardiogram

Unscheduled ECG measurements will be included in listings but will be excluded from tabular and graphical summaries by time point, except when calculating the maximum severity post baseline. Baseline is defined in [Section 3.1](#). Individual interval measurements and overall interpretations will be presented in [Listing 19](#) and [Listing 20](#), respectively.

---

The sort order for ECG interval measurements will be as follows: PR Interval, QRS Interval, QT Interval, QTcF Interval, RR Interval, and Ventricular Rate.

12-lead standard ECG results will be summarized in tables and figures:

- Summary of 12-lead standard ECG change in overall interpretation from baseline will be shown by treatment group and time point (**Table 38**).
- Number and percentage of participants with mild, moderate, severe, or life-threatening ECG results by parameter, time point, and treatment group (**Table 39**).

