**Table 39: ECG Results by Parameter, Severity, Treatment Group, and Time Point, Safety Population**

[Implementation Note: ECGs will be presented for Days -1 (baseline), 4, and 8 for each treatment group.

If there are no life-threatening/grade 4 vital signs reported, then the columns will be omitted. If there is not at least one graded event for a treatment group within a parameter, then only “Max Severity Post Baseline” will be shown. If there are more than one graded event within a parameter for a specified time point, then report the maximum severity.

Parameters will be shown in the following order: Any ECG Parameter, PR Interval, and QTcF Interval.]

Time Point	Treatment Group	N	None		Mild/ Grade 1		Moderate/ Grade 2		Severe/ Grade 3		Life-Threatening/ Grade 4	
			n	%	n	%	n	%	n	%	n	%
Any ECG Parameter												
Day -1 (Baseline)	400 mg SLV213		x	x	xx	x	xx	x	xx	x	xx	x
	Placebo											
	All Participants											
Day 4	400 mg SLV213											
	...											
Day 8	400 mg SLV213											
	...											
Max Severity Post Baseline	400 mg SLV213											
	...											
PR Interval												
Day -1 (Baseline)	400 mg SLV213		x	x	xx	x	xx	x	xx	x	xx	x
	Placebo											
	All Participants											
Day 4	400 mg SLV213											
	...											

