## 16.2.10 12-Lead Electrocardiogram

### Listing 19: 16.2.10: Electrocardiogram Interval Measurements

**[Implementation Note:** This included all ECG assessments, scheduled and unscheduled. These listings are not color-coded, but the severity should be included in parentheses after the result for abnormal results, e.g., 16.2 (Mild).

Refer to [Section 9.1.1](#) for sort order of ECG parameters.

Listing will be sorted by Treatment Group, Participant ID, Parameter, Time Point, and Assessment Time. Refer to [Section 9.1.1](#) for parameter sort order.]

Treatment Group	Participant ID	Sex	Parameter	Time Point	Assessment Date	Assessment Time	Result (Severity)	Change from Baseline
				Baseline	ddMMMyyyy	hh:mm		
				Day 4	ddMMMyyyy	hh:mm		

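### Minor: the QTcF-rise bands in SAP Table 9 and Protocol Appendix A give a 60 msec rise no change-based grade, so below a baseline of 420 msec it grades lower than a 59 msec rise

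*SAP*

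**What the plan says.** SAP Table 9 grades QTcF prolongation by absolute value and by rise from baseline, joined by OR:

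- Grade 1: 451–479 msec in men, 471–479 msec in women (absolute value only).
- Grade 2: 480–500 msec, or "increase in interval 30 – 59 msec above baseline".
- Grade 3: "QTcF >500 msec OR Increase in interval >60 msec above baseline".

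Protocol Appendix A, ECG Parameters, has the same Grade 2 bands and the same Grade 3 rule: "QTcF >500 msec OR increase in interval >60 msec above baseline". No other text in either document gives a rise of exactly 60 msec a change-based grade. In both tables the Grade 3 cell of the PR row also includes "Ventricular pause >3.0 msec".

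The grades are used in three planned outputs:

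- SAP Table 39 counts participants by ECG severity: "Parameters will be shown in the following order: Any ECG Parameter, PR Interval, and QTcF Interval".
- SAP Listing 19 prints the grade beside the reading: "the severity should be included in parentheses after the result for abnormal results". It also has a change-from-baseline column.
- SAP Section 9.9.2 and Table 14 count participants with at least one Grade 3 ECG parameter, which is part of the primary tolerability endpoint.

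**The concern.** A severity scale should not fall as the abnormality grows. Here the Grade 2 band stops at 59 and Grade 3 starts strictly above 60, so one whole-msec value belongs to neither. If the absolute QTcF does not supply at least Grade 2, a 60 msec rise is graded below a 59 msec rise, and one more msec takes it to Grade 3.

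A programmer who codes Table 9 literally will return none or mild for such a reading. One who notices the gap must pick a grade without a rule, possibly after seeing the data. The affected cells are the QTcF rows of Table 39 and the severity printed in Listing 19. Depending on which limit was intended, the Grade 3 ECG row of Table 14 could be affected too.

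**Working it through.** **Inputs.** The bands are those of SAP Table 9, which match Protocol Appendix A. The OR is read as keeping the higher of the absolute grade and the change grade. Protocol Section 8.1.1 requires QTcF within the Appendix A range at entry. The highest eligible baselines are therefore taken as 450 msec (men) and 470 msec (women), inferred from where Grade 1 starts. A floor of 330 msec is assumed. The result below 420 msec depends on neither ceiling.

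**Where the absolute bands take over at a rise of 60.** QTcF = baseline + 60.

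- Absolute Grade 2 needs QTcF ≥ 480, so baseline ≥ 480 − 60 = 420.
- Absolute Grade 3 needs QTcF ≥ 501, so baseline ≥ 501 − 60 = 441.
- Absolute Grade 1 starts at 451 − 60 = 391 (men) and 471 − 60 = 411 (women).

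**Grades at rises of 59 / 60 / 61 msec, as printed.**

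| Baseline, men | Baseline, women | 59 | 60 | 61 |
|---|---|---|---|---|
| up to 390 | up to 410 | 2 | none | 3 |
| 391–419 | 411–419 | 2 | 1 | 3 |
| 420–440 | 420–440 | 2 | 2 | 3 |
| 441 | 441 | 2 | 3 | 3 |
| 442–450 | 442–470 | 3 | 3 | 3 |

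Example: for a man with baseline 400, a QTcF of 459 is Grade 2, 460 is Grade 1 and 461 is Grade 3.

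**Full enumeration.** Over every whole-msec baseline from 330 to the ceiling and every rise from 0 to 120, the grade falls with increasing rise at one value only, 60 msec. It does so for baselines 330–419 in both sexes (419 − 330 + 1 = 90 values each).

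**Two ways to close the gap.**

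- 30–60 / >60: no falls remain. Only those 90 baselines per sex change, all at a rise of 60 and all to Grade 2. No baseline–rise pair changes Grade 3 status.
- 30–59 / ≥60: no falls remain on whole-msec data. A 60 msec rise becomes Grade 3 at every baseline up to 440, where the printed rule does not make it Grade 3 (440 − 330 + 1 = 111 baselines per sex).

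**How often it would arise.** Assume 16 participants (12 plus the 4 replacements in SAP Section 6.2), two scheduled post-dose ECGs each (Days 4 and 8), hence 32 readings, and a normal QTcF change with mean m and SD s. These m and s values are assumptions; the documents give none.

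Expected readings at 60 = 32 × [Φ((60.5 − m)/s) − Φ((59.5 − m)/s)]

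| m | s | Expected readings |
|---|---|---|
| 0 | 10 | 2.0e-8 |
| 0 | 15 | 2.9e-4 |
| 0 | 20 | 0.0071 |
| 10 | 20 | 0.028 |
| 20 | 20 | 0.086 |

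Protocol Section 8.1.1 allows QTcF to be calculated manually. If decimals are kept, the gap is every rise above 59 and up to 60. That interval is also 1 msec wide, so the expected count is of the same order.

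**Pause unit.** 3.0 msec is 0.003 s, in a row whose PR limits are 211–250 msec, so it cannot work as a Grade 3 limit. If seconds were meant, it is too small by a factor of 1,000. SAP Section 9.9.1 lists the measured parameters as "PR Interval, QRS Interval, QT Interval, QTcF Interval, RR Interval, and Ventricular Rate". Pause is not among them, nor among those in Table 39.

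**The case against.** The best counter-argument is that almost nothing turns on this. The top expected count, 0.09, needs a mean rise of 20 msec in everyone, placebo included. SAP Section 6.2 reports that dosing was discontinued in four participants, so 32 scheduled readings may be too many. Listing 19 would make a 60 msec rise visible. All of that stands. It sets the severity at minor but does not make the table right.

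A second argument is that both documents give a functional scale for adverse events the grading table does not cover, so an investigator could still grade the event. That may serve a reported adverse event. It does not supply the programmed QTcF grade in Table 39 or Listing 19.

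A third argument concerns the remedy, and it stands. The documents do not show whether the 59 or the >60 is the slip. The neighbouring bands meet in a way that favours 30–60 / >60: 480–500 then >500 in the same row, and tachycardia 116–130 then >130 in Table 7. But a whole-number band ending at 59 fits ≥60 just as well. The grading source has to decide.

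Two stronger readings are tempting. A reader might infer that the dose-halting rules were compromised. The dedicated QTcF halting criterion in Protocol Sections 7.1.1 and 7.1.2 uses the absolute limit of 500 msec and is unaffected. Other halting rules do use Grade 2 or 3 events, but SAP Section 2.1 says no further cohorts will be dosed. A reader might also infer that the pause limit would make almost any tracing Grade 3. Under Protocol Section 8.3.1 a clinician "will evaluate the ECG for any abnormalities in ECG intervals including QT/QTcF, and any morphologic abnormalities for clinical significance", and no planned table grades pause from a measurement, so no planned count is shown to be wrong.

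**Conclusion.** The QTcF-rise scale is wrong as written, in both documents. For every baseline below 420 msec, a 60 msec rise is ungraded or Grade 1, although 59 msec is Grade 2 and 61 msec is Grade 3. This is certain from the printed bands, given that the higher of the two grades is kept. The severity is minor: the likely effect is no reading or one, under the assumed 32 readings and normal change.

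It should not be read as showing that the Table 14 Grade 3 count is wrong. Under the printed limit a 60 msec rise is not Grade 3 by change, and closing the gap as 30–60 / >60 leaves that count alone. The count could move only if the source shows that ≥60 was intended. The finding rests on the QTcF gap alone; the pause unit is clerical.

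**What to change.** 1. Check the grading source for the QTcF-rise limits and the pause unit (probably seconds).
2. Make the rise bands in SAP Table 9 contiguous. If the printed Grade 3 limit is confirmed, use 30–60 (Grade 2) and >60 (Grade 3); no Grade 3 count changes. If the source says so, use 30–59 and ≥60, written as 30 to below 60 and ≥60 if decimals are kept. In that case, recheck the Grade 3 ECG row of Table 14.
3. Record the change in a SAP addendum before final data lock, listed among the changes from Protocol v4.0 in SAP Section 15. If lock has passed, Section 15 bars amending the SAP; use a note in the clinical study report, which the SAP Preface allows.
4. Check any investigator-assigned adverse-event grade at a 60 msec rise against the same rule. Protocol Section 8.5.4 leaves severity to the on-site investigator, so a SAP correction does not regrade those events by itself.
5. Correct the pause unit at the same time.

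The cost is a source check, a few cells in Table 9 and one entry in the record of changes. No new data or analyses are needed. Protocol Appendix A can wait until the protocol is amended for another reason or the table is reused, since an amendment needs IRB approval (Protocol Section 10.1). Until then the Section 15 entry, or the clinical study report note, documents the difference.

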## 14.1 Description of Study Participants

### 14.1.1 Disposition of Participants

**Table 10: Participant Disposition by Treatment Group, Full Analysis Population**

Participant Disposition	400 mg SLV213 (N=X)		Placebo (N=X)	
	n	%	n	%
Enrolled/Randomized	x	100	x	100
Included in Safety Population (Received at least One Dose of Study Product)	x	xx	x	xx
Included in the mITT Population (Received at least One Dose of Study Product and Meet Eligibility Criteria)				
Received All Planned Doses of Study Product a	x	xx	x	xx
Included in the PK Population b (Had at least One Quantifiable Post-Dosing Plasma Concentration)				
Completed all PK Blood Draws (Study Day 1 through Study Day 9)				
Completed Follow-up (Study Day 28) a				

Note: A total of X participants were screened from [study start date] to [date last enrollment].  
 N = Number of participants randomized (Full Analysis Population); n = Number of participants meeting the disposition criteria.  
a Refer to [Listing 2](#): 16.2.1 Early Terminations or Discontinued Participants for reasons participants discontinued or terminated early.  
b Refer to [Listing 5](#): 16.2.3 Participants Excluded from Analysis for reasons participants are excluded from the analysis populations.

**Table 11: Analysis Populations by Treatment Group, Full Analysis Population**

[**Implementation Note:** Participants can be counted for more than one reason. If no participants were excluded for the given reason, then that row will be omitted. If there is only one reason within a category, then “Any reason” row will be omitted. All analysis populations should be present. If there are no reasons within an analysis population, then only the “Any reason” row will be present for the category.]

Analysis Populations	Reason Participants Excluded	400 mg SLV213 (N=X)		Placebo (N=X)	
		n	%	n	%
Safety Population	Did not receive study product	x	xx	x	xx
mITT Population	Any Reason				
	Exclusion from Safety Population				
PK Analysis Population	Any Reason				
	Exclusion from Safety Population				
	No quantifiable post-dosing plasma concentration				

Note: N = Number of participants randomized (Full Analysis Population); n = Number of participants excluded entirely from the specified analysis population for the given reason.

### 14.1.2 Demographic Data by Study Group

**Table 12: Summary of Categorical Demographic and Baseline Characteristics by Treatment Group, Full Analysis Population**

[**Implementation Note:** If there are no records of “Other”, “Not Reported”, “Decline to State”, and “Unknown”, then the characteristics will be omitted, respectively.]

Variable	Characteristic	400 mg SLV213 (N=X)		Placebo (N=X)	
		n	%	n	%
Sex	Male	x	xx	x	xx
	Female				
Sex Assigned at Birth	Male				
	Female				
	Intersex				
Gender Identity	Cisgender Man				
	Cisgender Woman				
	Genderqueer				
	Gender Non-binary				
	Gender Non-conforming				
	Transgender Man				
	Transgender Woman				
	Other				
	Decline to State				
Ethnicity	Not Hispanic or Latino	x	xx	x	xx
	Hispanic or Latino				
	Not Reported				
	Unknown				
Race	American Indian or Alaska Native	x	xx	x	xx
	Asian				
	Native Hawaiian or Other Pacific Islander				
	Black or African American				
	White				
	Multi-Racial				
	Unknown				

Note: N = Number of participants randomized (Full Analysis Population); n = Number of participants with the given characteristic.

**Table 13: Summary of Continuous Demographic and Baseline Characteristics by Treatment Group, Full Analysis Population**

Variable	Statistic	400 mg SLV213 (N=X)	Placebo (N=X)
Age (years)	Mean (SD)	xx.x	xx.x
	Median	xx.x	xx.x
	Minimum, Maximum	xx, xx	xx, xx
Weight (kg)	Mean (SD)	xx.xx	xx.x
	Median	xx.xx	xx.x
	Minimum, Maximum	xx.x, xx.x	xx, xx
Height (cm)	Mean (SD)	xx.xx	xx.x
	Median	xx.xx	xx.x
	Minimum, Maximum	xx.x, xx.x	xx, xx
BMI (kg/m  )	Mean (SD)	xx.xx	xx.x
	Median	xx.xx	xx.x
	Minimum, Maximum	xx.x, xx.x	xx, xx

Note: N = Number of participants randomized (Full Analysis Population).

SD = Standard Deviation.

## 14.2 Tolerability Data

**Table 14: Tolerability by Treatment Group, Safety Population**

Participants who:	400 mg SLV213 (N=X)		Placebo (N=X)	
	n	%	n	%
Terminated early or withdrawn due to TEAE related to study product	x	xx	xx	xx
Have at least one TEAE				
Met Grade 3 abnormal criteria at least once post-dose for				
Safety laboratory tests				
VS measurements				
Safety ECG parameters				
Completed all oral medication doses				

Note: N = Number of participants in the Safety Population; n = Number of participants meeting each tolerability category criteria.

### 14.3 Pharmacokinetic Data

**Table 15: Summary Statistics for SLV213 Concentrations in Plasma, 400 mg SLV213 PK Population – Day 1, Morning Dose (Single Dose)**

[**Implementation Note:** SLV213 plasma concentrations will be summarized for Study Day 1 for 400 mg SLV213 treatment group. Nominal time points are t=0, 0.5, 1, 2, 4, 6, 8, and 12 hours post morning dose.]

Statistic	Nominal Time a (h)							
	0	0.5	1	2	4	6	8	12
n	x	x	x	x	x	x	x	x
Mean (SD)	xx.x (xx.x)	xx.x (xx.x)	xx.x (xx.x)	xx.x (xx.x)	xx.x (xx.x)	xx.x (xx.x)	xx.x (xx.x)	xx.x (xx.x)
Geometric Mean	xx.x	xx.x	xx.x	xx.x	xx.x	xx.x	xx.x	xx.x
CV%	xx.x	xx.x	xx.x	xx.x	xx.x	xx.x	xx.x	xx.x
Median	xx.x	xx.x	xx.x	xx.x	xx.x	xx.x	xx.x	xx.x
Minimum, Maximum	xx, xx	xx, xx	xx, xx	xx, xx	xx, xx	xx, xx	xx, xx	xx, xx

Note: Concentrations are reported in units of ng/mL. Time points where data was not collected are denoted by “-”. Time points where data was not estimable are denoted by “NE”.

BQL values were imputed as 0 if they did not come after a PK sample concentration that is above the LLOQ. The first BQL value after the last PK sample concentration that is above the LLOQ is imputed as  $\frac{1}{2}$  LLOQ. All other BQL values are treated as missing.

n = Number of data points used to compute summary statistics.

SD = Standard Deviation; CV = Coefficient of Variance.

a Times are relative to time of dosing. Time 0 concentrations are drawn within 30 minutes prior to dosing.

